Any adverse events that occur during the test should be recorded in detail.

(1) Large dose of creatine supplement may cause muscle stiffness, spasm and other adverse phenomena.

(2) Exceeding recommended doses of curcumin can cause nausea and even vomiting and diarrhea.

None of the doses used in this study exceeded the recommended dose, so the probability of adverse events was small. Once adverse events occur, the oncologist and nutritionist will be reported immediately, and the current intervention will be suspended according to the actual condition of the patient, and the treatment measures will be developed.

7. Research on quality control and quality assurance

(1) Laboratory quality control measures

The standard operating procedures and quality control procedures for experimental observation indicators should be established in hospital laboratories.

(2) Training of researchers

Prior to the commencement of clinical trials, the investigator should be trained in the protocol.

(3) Measures to improve subject compliance

① The researcher should carefully perform informed consent so that the subjects can fully understand the test requirements and cooperate with the test.

(2) Pay attention to the number of days of experimental drugs, whether there is intermittent drug use, and monitor the compliance of subjects.

Compliance = actual number of days of medication/number of days of medication × 100%

Compliance is 80% ~ 120% compliance is good; Compliance is poor if less than 80% or more than 120%.

(4) Oversight of clinical trials

Monitoring of patients' actual nutrient intake during nutritional therapy:

Follow-up: The patients were discharged from the hospital for routine dietary guidance, with daily total energy set at 30-35kcal /kg.d and daily protein intake at 1.0-2.0 g/kg.d, and continued to receive total nutrition preparations and/or whey protein oral nutrition supplement or tube feeding enteral nutrition supplement.

Monitoring of patients' condition during the experiment:

When the patients included in the study experience changes or even adverse reactions, strict diagnosis and treatment will be taken immediately to avoid the occurrence of adverse events.

8. Data security audit

The clinical study will develop a data safety monitoring plan according to the risk. All adverse events are recorded in detail, properly handled and tracked until properly resolved or the condition is stable, and serious adverse events and unexpected events are reported to the Ethics Committee, competent authorities, sponsors and drug regulatory authorities in a timely manner in accordance with regulations; The principal investigator conducts regular cumulative reviews of all adverse events and holds investigator meetings where necessary to assess study risks and benefits; For studies with greater than minimum risk, an independent data monitor will be assigned to monitor the study data. For high-risk studies, an independent Data Safety Monitoring committee will be established to monitor the accumulated safety and efficacy data and make recommendations on whether to proceed.

9. Statistical analysis

Statistical analysis was performed using GraphPad Prism version 8.0 (La Jolla, CA, USA). Student's t-test was used for comparison between groups, and one-way analysis of variance (ANOVA) was used for other data. All data are presented as mean \pm SEM. $p < 0.05$ (*) indicates statistical significance. $p < 0.01$ (**) indicates that the difference is more statistically significant.

10. The ethics of clinical research

Clinical research will follow the relevant regulations such as the Declaration of Helsinki of the World Medical Congress. Clinical studies are conducted only after the protocol is approved by the Ethics Committee prior to the start of the study. Before each subject is enrolled in this study, the investigator is responsible to give a complete and comprehensive introduction of the purpose, procedure and possible risks of this study to the subject or his/her agent and sign a written informed consent. Subjects should be informed that they have the right to withdraw from this study at any time, and informed consent should be kept as a clinical study document for future reference. Subjects' privacy and data confidentiality will be protected during the study.

11. Research schedule

Jun 1,2023 to Aug 31,2023: The formal implementation of the project was started. 76 cases were collected, and baseline investigation was conducted for enrolled patients. The patients were not randomly enrolled, and grouped intervention was performed.

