
plan
	
use.
 
(2) General investigation: dietary investigation, digestive tract symptoms, height, weight.
 
(3) Nutritional assessment: NRS2002 and PG-SGA scores, grip strength, body composition, grip strength, deltoid skin fold thickness, upper arm muscle circumference.
 
(4) Examination and examination: blood routine, biochemical set, IL-6, TNF-α, lactic acid, serum insulin, prealbumin, transferrin, chest, and abdominal CT, PETCT, etc.
 
(5) Functional Assessment of Anorexia/Cachexia Therapy (FAACT);
 
(6) QoL Evaluation Scale: ADL scale.
 
After informed consent, patients were divided into groups A and B according to their wishes.
 
Group A: According to the national industry health standard "Dietary Guidance for Patients with Malignant Tumors 2017", basic nutrition treatment, energy 30 ~ 35kcal/kg, protein 1.0-2.0g/kg, diet deficiency, total nutrition and/or whey protein oral nutrition supplement or tube feeding enteral nutrition.
 
Group B: Since basic nutrition in group A, creatine 5g/d and curcumin 4g/d were added orally for one month.
 
2. follow-up
 
Weekly telephone follow-up, 2 weeks of routine outpatient follow-up, general condition survey, nutritional intake, nutritional assessment, routine examination, anorexia/fluid therapy functional assessment, QoL rating scale, 4 weeks of effectiveness evaluation, 3 months of survival survey.

Evaluation of curative effect
	
Efficacy evaluation indicators (primary efficacy indicators and secondary efficacy indicators)
 
Main research Indicators
 
(1) Nutritional serum indexes: blood routine, biochemical complete set, prealbumin, transferrin
 
(2) Body composition index: skeletal muscle index and body composition in L3 section of CT scan
 
(3) Inflammatory metabolism indicators: serum insulin, IL-6, TNF-α, lactic acid, PETCT to evaluate the metabolism
 
Secondary study indicators
 
(1) Physical measurements: body weight, grip strength, triceps skin fold thickness, upper arm circumference diameter
 
(2) Nutritional assessment: energy and protein intake, PG-SGA score
 
(3) Functional Assessment of Anorexia/Cachexia Therapy (FAACT)

	
(4) QoL evaluation scale: ADL score
 
(5) Survival time survey: 1, 3 months survival rate
 
(6) Evaluation of tumor efficacy: Compared with the baseline at the time of enrollment, tumor remission and progression were compared

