1.3 Research to be carried out.

In this review, cachexia is a common complication of various advanced malignant tumors, which seriously affects the quality of life and survival time of patients. In view of the clinical problem of non-nutritional response in patients with cachexia, we plan to carry out a clinical case-control study on the intervention of creatine combined with curcumin in patients with cachexia. Overall, we limited the study subjects to upper digestive tract tumors and diagnosed patients with early cachexia. The main purpose of this study is to determine whether the combination of the two can play a positive and stable role in inhibiting the inflammation of cachexia and improving metabolic status, so that basic nutrition can play a role, to reduce the level of skeletal muscle consumption, maintain weight, improve quality of

life, save medical costs, and extend survival time.

2. Purpose of the study

(1) To investigate whether creatine combined with curcumin can improve the inflammatory state, correct the disorder of nutrient metabolism and improve the nutritional status in the early cachexia stage of upper gastrointestinal neoplasms.

(2) To investigate whether creatine combined with curcumin can improve the quality of life and prognosis of patients with early cachexia in upper digestive tract tumors.

3. Study design type, principle, and test procedure

(1) Study Design

Type of study design: prospective open controlled clinical trial; Non-random grouping method: According to the exclusion criteria, patients were included into group A or group B according to their wishes after informed consent; Blind level: This experiment is an open study without blind or emergency letters. Research Center: None.

Group A: basic nutrition treatment, energy 30-35 kcal/kg, protein 1.0-2.0 g/kg, diet deficiency, total nutrition and/or whey protein oral nutrition supplement or tube feeding enteral nutrition supplement.

Group B: Since basic nutrition in group A, creatine 5g/d and curcumin 4g/d were orally added, and the intervention time was 1 month.

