It was assumed that after 4 weeks of oral administration of creatine + curcumin in group B, combined with the existing literature on the improvement of the quality of the bad fluid, the skeletal muscle index at L3 section of CT scan in group B was 20% higher than that in control group A, and the standard deviation was 14%. Bilateral test was required, α was 0.05, the sample ratio between the two groups was 1:1 (i.e., the number of cases in the two groups was equal), $\beta=0.2$. The degree of assurance (test efficacy) $1-\beta=80\%$ was calculated using SPSS software, then the sample size of each group was 68 cases, considering the 10% loss of follow-up rate, each group needed 76 cases, 152 patients in total.

Follow-up test item time point

Classification	Item	0	0.5m	1m	3m
Serological indicators	blood routine	√	-	√	√
	biochemical set	√	-	√	√
	prealbumin	√	-	√	√

	transferrin	√	-	√	√
Body composition index	CT scans skeletal muscle index at L3 cross section	√	-	√	√
	BIA measures muscle mass	√	-	√	√
Inflammatory metabolic indicators	Serum insulin	√	-	√	√
	IL-6	√	-	√	√
	TNF- α	√	-	√	√
	lactic acid	√	-	√	√
	PETCT (SUV)	p.r	-	p.r	-
Physical measurements	Weight	√	√	√	√
	grip strength	√	√	√	√
	skin fold thickness	√	√	√	√
	upper arm circumference	√	√	√	√
nutrition assessment	intake	√	√	√	√
	PG-SGA score	√	√	√	√
Questionnaire Survey	Functional Assessment of Anorexia/Cachexia Therapy(FAACT)	√	√	√	√
	ADL evaluation scale	√	√	√	√

4. Criteria

Inclusion Criteria:

(1) Clinical diagnosis of advanced tumors of the upper digestive tract with untreatable or postoperative recurrence of esophageal and gastric cancer III-IV

- (2) Meet the diagnostic criteria of early cachexia (anorexia and metabolic changes, involuntary body mass reduction $\leq 5\%$ within 6 months)
- (3) Radiotherapy, chemotherapy, or immunotherapy in our hospital
- (4) Understand and fill in a variety of rating scales
- (5) Informed consent, voluntary participation in this study

Exclusion Criteria:

- (1) Neoadjuvant chemotherapy patients
- (2) Intestinal obstruction or gastrointestinal bleeding
- (3) Severe heart, lung and renal insufficiency
- (4) Coagulopathy
- (5) Clinical diagnosis with diabetes and other metabolic diseases
- (6) The expected survival time is less than 1 month
- (7) With cognitive dysfunction or poor coordination
- (8) Allergy to creatine or curcumin
- (9) With a history of drug abuse
- (10) Doctors or researchers deem unsuitable for study participation

Removal Criteria:

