- (1) Do not meet the inclusion criteria and mistakenly included or meet any of the exclusion criteria.
- (2) Meet the inclusion criteria but did not use after inclusion or did not have any record of return visit.
- (3) The intervention measures used during the trial did not conform to the protocol.

Criteria for study termination:

- (1) With allergic reactions or serious adverse events should be stopped according to the investigator's judgment.
- (2) Other complications and special physiological changes occurred during the test.
- (3) During the experiment, the subjects needed parenteral nutrition support during the nutritional support process, and the experiment should be stopped.
- (4) Poor compliance.
- (5) Pregnancy.

5. Research methods and technical route

(1) Research food names and specifications

The creatine provided to the patient in this experimental study scheme was purchased from the sports nutrition food Decathlon creatine powder (powder: 10g/ packet *10 packets/box) produced by Jiangsu Alante Nutrition Co., LTD. Purchased from Meriva Curcumin Phytosome (capsule: 1g/ capsule *120 capsules/box) from THORNE Company, USA.

(2) Treatment plan

Clinical data of patients with advanced esophageal and gastric cancer combined with early cachexia were collected, abdominal CT scan was performed, and the skeletal muscle area and

density of L3 section were measured by Matlab software. Skeletal muscle index was obtained after height correction, and body composition and bone mineral density were measured at the same time. Routine examination and nutritional indexes were determined, including blood routine, biochemical set, prealbumin, transferrin; Inflammatory metabolic markers including serum insulin, IL-6, TNF- α , lactic acid, and PETCT were assessed for metabolism. NRS2002 and PG-SGA scores were performed. According to the standard body weight, dietitians formulated diets for all enrolled patients. According to the ESPEN guidelines and the national industry health standard "Dietary Guidelines for Patients with Malignant Tumors 2017", the dietary energy intake standard was 30-35kcal /kg·d, and the protein intake was 1.0-2.0g /kg·d. The deficiency was given to oral enteral nutrition supplements or whey protein supplements, or to patients requiring tube feeding. Patients were enrolled in group A control group or group B intervention group on a voluntary basis.

Group A intervention group: The above basic nutritional support was provided.

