Group B control group: In addition to the above basic nutrition, oral creatine powder 5g qd, curcumin capsule 2g bid for one month.

The intake, complications and survival of the patients were followed up by telephone for 1 and 3 weeks, physical indicators, nutritional assessment, FAACT and QoL scale were followed up for 2 weeks in the hospital and outpatient department, and nutritional serum indicators, body composition indicators, inflammatory metabolism indicators, physical indicators, nutritional assessment were reviewed for 4 weeks. Evaluation of effect. The long-term survival, re-hospitalization and hospitalization expenses were investigated 3 months later. To evaluate the effect of creatine combined with curcumin on improving the nutritional status, metabolic level and clinical prognosis of alimentary tract neoplasm. Note: Weight is calculated by standard weight: Standard weight (kg) = height (cm)-105.

(3) Combination of drugs

During the study period, patients may have been treated with chemotherapy drugs and immunotherapy drugs due to tumor treatment and may have taken megestrol orally against the oxalic fluid to improve appetite. To avoid the influence of the two groups of therapeutic drugs, the diseases, and drugs of the two groups will eventually be grouped and stratified to eliminate the interference of combined drug use.

(4) Safety evaluation index

- ① Incidence and severity of side effects
- ② The rate of unplanned rehospitalization.

6. Observation of adverse events

Adverse Event (Adverse Event): An adverse medical event occurs after a patient or clinical trial subject receives a drug or a formula for a special medical use, but there is not necessarily a causal relationship.

Serious Adverse Event: An event occurs during the clinical trial that requires hospitalization, prolongates the hospital stay, causes disability, affects the ability to work, threatens life or death, or

results in congenital malformations.

Adverse reaction: an adverse reaction that is harmful rather than expected but is causally related to the application of a drug or special medical use formula food during normal application of the drug or special medical use formula food at prescribed doses. In clinical trials for a new use, all reactions that are harmful and not causally related to the use of a drug or a formula for special medical use, as expected, should be considered adverse when the dose has not been determined.

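### Patients choose their own group, yet the analysis section names only unadjusted tests, so a significant result may reflect who chose the supplements

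*Combined protocol and SAP*

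**What the plan says.** Group membership is the patient's choice. Section 3(1) calls the grouping non-random and says "patients were included into group A or group B according to their wishes after informed consent". The Summary (treatment plan) says "patients were divided into groups A and B according to their wishes", and section 5(2) says "Patients were enrolled in group A control group or group B intervention group on a voluntary basis". The study is open.

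The analysis is given in section 9 and repeated in the Summary (method of statistics): "t-test was used for comparison between groups, and one-way analysis of variance (ANOVA) was used for other data". Neither place mentions a baseline value, covariate, stratum, matching or weighting. Neither says whether the 4-week value or the change from baseline is tested. The sample size paragraph in section 3 assumes that after 4 weeks "the skeletal muscle index at L3 section of CT scan in group B was 20% higher than that in control group A", which does not settle that question.

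One sentence elsewhere bears on confounding. Section 5(3) says "the diseases, and drugs of the two groups will eventually be grouped and stratified to eliminate the interference of combined drug use".

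The stated aim in section 5(2) is causal: "To evaluate the effect of creatine combined with curcumin on improving the nutritional status, metabolic level and clinical prognosis of alimentary tract neoplasm".

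**The concern.** A two-sample t-test supports a statement about the supplements only if the two groups would otherwise have had the same outcomes. Randomisation would justify that; patient choice does not. Patients who opt for two extra oral supplements may differ from those who decline in muscle mass, intake, nutritional status, inflammation or motivation. Section 1.1 itself links inflammation to increased catabolism, so a baseline difference in inflammation could predict later muscle loss whichever supplements are taken.

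The stratification sentence in section 5(3) does not close the gap. It names no strata, method or outcomes, and it does not appear in section 9. It leaves out baseline muscle index, intake, nutritional status and inflammation. Its lead-in, "During the study period, patients may have been treated with chemotherapy drugs and immunotherapy drugs due to tumor treatment", also leaves open whether drugs started after group choice would be used, and those could themselves be affected by group.

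Because the form of the outcome is unstated, raw values or changes can be chosen after the data are seen. Section 11 schedules a statistical analysis, and possible changes to the programme, after the first 76 patients. The central comparison for every continuous outcome is affected.

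**Working it through.** **The plan's own figures.** Section 3 gives 68 evaluable per group, 10% loss, two-sided α of 0.05, 80% power, a 20% difference and an SD of 14%. The loss step reproduces: 68/0.9 = 75.6, so 76 per group and 152 in total. The 68 does not: 2 × (1.960 + 0.842)² / (20/14)² = 7.7, so 8 per group (9 with the exact t). That is a separate matter. I use 68 because it is the planned evaluable number.

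**Assumed inputs (none is in the documents).** No true effect; a baseline gap g in L3 skeletal muscle index (L3 SMI) of 0.3 SD, with 0.2 and 0.4 as a range; baseline-to-4-week correlation r of 0.9, 0.7 or 0.5; unit SD at both times. Two models are considered, since the documents do not settle which holds:

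- Model 1, groups regress to a common mean: 4-week gap = r·g.
- Model 2, each group keeps its own mean: 4-week gap = g.

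**Formulas.** For a t-test with standardised difference d, the non-centrality is d·√(68/2) = 5.83·d on 134 degrees of freedom.

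- Raw 4-week value: d = r·g (Model 1) or g (Model 2).
- Change: mean difference −(1−r)·g with SD √(2(1−r)), so |d| = g·√((1−r)/2) (Model 1), or 0 (Model 2).
- Baseline-adjusted model (ANCOVA): expected bias 0 (Model 1) or g·(1−r) (Model 2). Rejection rates are by simulation, 40,000 trials per scenario.

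Worked case, Model 1, r = 0.9: d = 0.9 × 0.3 = 0.27 and non-centrality 1.57, giving a rejection rate of 34.6%.

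**False-positive rates, g = 0.3 (r = 0.9 / 0.7 / 0.5)**

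| Analysis | Model 1 | Model 2 |
|---|---|---|
| Raw 4-week t-test | 35% / 23% / 14% | 41% at every r |
| Change t-test | 7% / 10% / 14% | 5% |
| ANCOVA | about 5% | 6.8% / 11.0% / 16.5% |

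The raw test at other gaps: g = 0.2 gives 18% / 13% / 9% (Model 1) and 21% (Model 2); g = 0.4 gives 55% / 37% / 21% and 64%.

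**Adding an unmodelled 0.1 SD shift in outcome between choosers, g = 0.3**

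| Shift | Analysis | Model 1 | Model 2 |
|---|---|---|---|
| With the gap | Raw | 57% / 43% / 30% | 64% |
| | Change | 15% / 5% / 6% | 25% / 12% / 9% |
| | ANCOVA | 26% / 13% / 10% | 40% / 33% / 38% |
| Against the gap | Raw | 17% / 10% / 6% | 21% |
| | Change | 39% / 29% / 30% | 25% / 12% / 9% |
| | ANCOVA | 26% / 12% / 10% | 15% / 5% / 6% |

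ANCOVA and change are both significant in the same direction in about 3% of trials with no shift, and in 2% to 26% with one.

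**In points.** If the 14% is read as the SD of 4-week L3 SMI (an assumption), the smallest significant difference is 1.978 × 14 × √(2/68) = 4.7 points. A 0.3 SD gap alone adds 14 × 0.3 × r = 3.8 / 2.9 / 2.1 points (Model 1) or 14 × 0.3 = 4.2 points (Model 2) to the raw difference.

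No figure models the section 5(3) stratification, because it gives no strata or method.

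**The case against.** The strongest reply concerns size and remedy.

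- **The high rates need a raw-value test.** The plan does not commit to one, and on a change reading the rates at a 0.3 SD gap are 5% to 14%. The gap, the correlation and the model are all assumed. This stands: what is certain is the omission, not any one rate. But leaving the choice open is itself part of the fault.
- **The bias is small beside the planned effect.** A contribution of 2.1 to 4.2 points is 11% to 21% of the planned 20%, so such a gap could not alone explain a result of that size. This also stands. The risk lies mainly with smaller differences, and anything above about 4.7 points would be declared significant.
- **The remedy does not always win.** Under Model 1 with a shift against the gap, both proposed analyses reject at least as often as the raw test, and at r = 0.9 they agree falsely in about 26% of trials. Under Model 2 with no shift, change does better than ANCOVA. This is correct, and it is why two analyses and softened wording are needed.
- **Equal groups are not guaranteed.** At 100:36 with g = 0.3, the raw rates fall to 28% / 19% / 12% (Model 1) and 34% (Model 2). The size changes, but the point does not.
- **Section 5(3) shows some intent to handle confounding.** It does, but it is unspecified, is aimed at combined drug use, and is missing from section 9.

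**Conclusion.** The concern holds and should be fixed before analysis. Groups are self-selected, the only tests named are unadjusted, and the stated aim is to evaluate an effect. That much follows from the text without any assumption.

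The size is conditional. With 68 per group and no true effect, a raw 4-week test has a false-positive rate of 9% to 21% at an assumed 0.2 SD baseline gap and 14% to 41% at 0.3 SD, across correlations of 0.5 to 0.9 and both models. A change analysis at 0.3 SD gives 5% to 14%. The documents give neither the size nor the direction of any difference between choosers. An unmeasured difference of only 0.1 SD can push every candidate analysis well above 5%.

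**What to change.** In section 9, prespecify the following:

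1. **Main analysis for L3 SMI** (the outcome behind the sample size): a linear model of the 4-week value on group, baseline L3 SMI and a short list of enrolment factors. These are tumour site, stage, type of anticancer treatment, PG-SGA, energy and protein intake, IL-6 and TNF-α, and megestrol use at enrolment. Use the same form, with its own baseline value, for the other continuous outcomes.
2. **Sensitivity analysis**: the same covariates in a model of change from baseline, without the baseline outcome term. Report both, and give the reason for making the first one primary. Agreement is informative but not proof; disagreement should be reported as dependence on the assumption.
3. **Section 5(3) carried into section 9**, using disease and drug status at enrolment only.
4. **A table of baseline characteristics by group**, with conclusions worded as adjusted associations.

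Survival and tumour remission or progression need their own methods and are outside this point.

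The cost is analysis-plan wording and two regressions in place of a t-test. No new assessments are needed. Stage, treatment, drug use, diet, PG-SGA, IL-6 and TNF-α are in the Summary's baseline investigation, and L3 SMI is scheduled at 0 and 1 month. Tumour site follows from the eligibility diagnosis. Megestrol is not listed by name, so the sponsor should confirm that the drug-use record captures it.

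The full model has about 13 to 14 coefficients for 2 × 68 = 136 patients, roughly 10 patients each, so the list should not grow. Unmeasured confounding such as motivation remains, and the causal wording has to be softened.

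### The stated inputs (20% difference, SD 14%, two-sided 0.05, 80% power, 1:1) give 8 or 9 patients per group, not 68, so the effect behind the 152 patients cannot be identified

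*Combined protocol and SAP*

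**What the plan says.** The sample size paragraph in Section 3 (Study design type, principle, and test procedure) sizes the trial on the L3 skeletal muscle index from CT after 4 weeks of supplementation. It assumes that the index "in group B was 20% higher than that in control group A, and the standard deviation was 14" per cent. The test is two-sided with alpha 0.05 and beta 0.2 (80% power), and "the sample ratio between the two groups was 1:1". SPSS is named as the software. The result is: "then the sample size of each group was 68 cases, considering the 10% loss of follow-up rate, each group needed 76 cases", or 152 in total.

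Section 9 (Statistical analysis) names the between-group test: "Student's t-test was used for comparison between groups". Item (1) of Section 3 describes allocation: "patients were included into group A or group B according to their wishes after informed consent".

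The paragraph gives no formula and no control-group mean, and it does not say what the 14% is a percentage of. It refers to existing literature in general terms but cites nothing for the 20% or the 14%.

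**The concern.** The paragraph supplies every input that a standard comparison of two means needs, so 68 should follow from them. A difference larger than one standard deviation normally needs very few patients, and 68 per group is typical of an effect near half a standard deviation. At least one of the difference, the SD (its value or its unit) and the n must therefore be misstated.

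This paragraph is the only justification in the documents for enrolling 152 patients with advanced cancer. If it does not hold together, an ethics committee cannot check that number, and a reader of a null result cannot tell which effect the trial was able to exclude.

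**Working it through.** **Inputs.** From the Section 3 sample size paragraph: difference 20%, SD 14%, two-sided alpha 0.05, power 80%, ratio 1:1, loss 10%. From Section 9: Student's t-test. Assumption: the 20% and the 14% are on the same scale, as printed.

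**1. The dropout step reproduces.** 68/(1 − 0.10) = 75.6, rounded up to 76; 2 × 76 = 152. The problem lies in the 68.

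**2. The 68 does not reproduce.**
- Standardised difference: d = 20/14 = 1.429.
- Normal approximation: n = 2(1.960 + 0.842)²/d² = 2 × 7.849/2.041 = 7.69, so 8 per group.
- Noncentral t, matching the planned test: 8.76, so 9 per group (power 0.757 at 8 and 0.812 at 9).
- After 10% loss: 9/0.9 = 10 per group, 20 in total.
- Ratio to the stated figure: 68/9 = 7.6 and 68/8 = 8.5, about eight-fold.

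**3. Power at the stated n.** With 68 per group and d = 1.429, power exceeds 99.99%.

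**4. What 68 per group implies at 80% power.** The noncentral t gives d = 0.484.
- If the SD is 14%: difference = 0.484 × 14 = 6.8 points.
- If the difference is 20%: SD = 20/0.484 = 41%.

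**5. Other readings as a comparison of means (n per group).**

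| Reading | n |
|---|---|
| One-sided test | 7 |
| 90% power | 11–12 |
| 99% power | 19–20 |
| Log-ratio scale, CV 14% | 10–11 |
| SD proportional to each arm's mean | 10 |
| SD inflated to 14√2 | 16 |
| Difference and SD swapped | 33–34 |
| Bonferroni for 50 tests | 17 |

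None gives 68.

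**6. Two readings that do come close, both by changing the text.**
- *SD 14 in absolute units, 20% relative to the control mean.* The difference needed is 6.78 units, so the control mean would be 6.78/0.20 = 33.9. No control mean is given, and the SD is printed as a percentage. By the t-test, assumed means of 30, 34, 40, 45 and 55 give 87, 68, 50, 39 and 27 per group.
- *14% against 34% as proportions.* The unpooled formula gives (0.14 × 0.86 + 0.34 × 0.66) × 7.849/0.20² = 67.7, so 68. This does not fit a continuous index with an SD, or a t-test.

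**7. Equal groups (illustrative splits, SD 14% assumed).** If 136 evaluable patients divide 90:46 or 100:36, power for 6.8 points falls from 80% to 76% or 70%. The difference detectable with 80% power rises to 7.2 or 7.7 points.

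**The case against.** The plan does name a target: an index 20% higher at 4 weeks. It can be argued that only the scale of the SD and the route to 68 are lost, and that the figure of 8 or 9 depends on both percentages sharing a base, which the text does not say. The assumption is noted, but it does not rescue the paragraph. The readings that reach 68 use different scales or a different kind of endpoint, so they imply different effects, and nothing in the documents chooses between them.

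A second argument is that 152 is ample, so no harm follows. That is true if 20% and 14% are right. If 68 was correctly derived from other inputs, the target is an effect near half a standard deviation and there is no surplus.

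Three narrower points stand:
- The figure of 20 patients applies to one index under an unadjusted t-test. It ignores the other main indicators in the Summary and the stratification by disease and drugs in Section 5(3). It shows the inconsistency and is not a proposed sample size.
- The unequal splits are illustrative, and no imbalance is documented. For the effect as stated (d = 1.43), even a 126:10 split keeps about 99% power. Allocation matters only if the real target is the smaller effect.
- The literature is mentioned as a basis, and the wording suggests a 4-week level rather than a change from baseline. The fair criticism is that there is no citation and that the SD is not tied to either quantity.

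**Conclusion.** The concern holds. With the printed inputs on one scale, the requirement is 8 or 9 per group against 68 stated, about an eight-fold discrepancy that no ordinary variant of a two-mean calculation removes. At 80% power, 68 per group corresponds to d = 0.48, about a third of the stated 1.43.

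Which figure is wrong cannot be settled from the documents. The trial is not shown to be too small for its stated effect; on the stated inputs it is far larger than this endpoint needs. The defect is that the sole justification for 152 contradicts itself, and it must be corrected. The assumption of equal groups, which allocation by patient wish does not secure, is a secondary point.

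**What to change.** Retrieve the original SPSS entry and rewrite the paragraph so that difference, SD, n and power agree. Suggested wording:

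> The sample size assumes a control-group mean L3 skeletal muscle index of [value, unit] at 4 weeks, a difference of [value, same unit] and an SD of [value, same unit; 4-week level or change from baseline], from [source]. With a two-sided t-test at 0.05 and equal groups, [n] evaluable patients per group give [power].

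Only if an SD of 14% on the same scale as the difference is confirmed, state that 68 evaluable patients per group give 80% power for a difference of about 6.8 percentage points, and say whether that difference is plausible and worthwhile. It should not be adopted merely because it fits the n.

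Add one sentence saying that the calculation assumes equal groups, that allocation by patient wish does not ensure this, and that power will be restated for the group sizes obtained. Confidence intervals in the report will show the precision reached.

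Nothing here calls for a change to the planned 152. If the look-up shows inputs that need a different number, the bracketed n and power must say so. The cost is one look-up and one paragraph of protocol wording; at least one stated figure (difference, SD or its unit, n, or power) will change.
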